6.3.2 Protocol Deviations

All protocol deviations will be collected on CRF and will be listed by subject including start date, end date and impact of deviation. Study day will be presented along with start and end date of deviation.

6.3.3 Background and Demographic Characteristics

Descriptive statistics (sample size, mean, median, standard deviation [SD], minimum [Min] and maximum [Max]) will be presented for continuous variables: age, height, weight and body mass index [BMI]. Frequency counts and percentages will be tabulated for categorical variables: age group (<18, 18-40, 41-65, and > 65 years), gender, ethnicity, and race.

Results will be presented for the safety population.

All demographic characteristics will be listed by subject.

6.3.4 Study Drug Administration

The study drug administration details (start/end date, start/end time) will be listed by subject. The dosing time will be set to the time the film is placed on the center of the top surface of the tongue. The total time taken for complete dissolution of film will be recorded in seconds and listed by subject.

6.3.5 Prior and Concomitant Medications and Therapies

The World Health Organization Drug Enhanced (WHO DDE) Version Jun2016, format B2 will be used to classify all medications reported during the study to an Anatomical Therapeutic Chemical (ATC) Level 1 term and a standardized medication name.

Prior medication is any medication/therapy stopped prior to the study drug administration, regardless of medication start date. Concomitant medication is any medication started and not stopped before the study drug administration.

Concomitant Medications will be summarized by Anatomical Therapeutic Chemical (ATC) category Level 1 and by standardized medication name. ATC Level 1 categories and standardized medication names will appear in an alphabetical order on the summary table. For each medication, the number of subjects and percentages will be displayed.

The use of prior and/or concomitant medication will be listed by subject.

6.3.6 Medical Histories

Medical history will be collected at screening and reviewed for any exclusionary criteria. The Medical Dictionary for Regulatory Activities (MedDRA[®]) Version 19.1 will be used to classify all medical history findings to a System Organ Class (SOC) and Preferred Term (PT).

All medical history data will be listed and sorted by subject and alphabetically according to SOC and PT

6.4 Efficacy Analysis

No efficacy analysis is planned as per the protocol. This is a single dose safety study with no measurement of efficacy.

6.5 Safety Analysis

Safety data will be evaluated through the assessment of PAS scores on the VFSS, adverse events (AEs), clinical signs and symptoms from physical and neurological examination following study drug administration, and vital signs assessments. Treatment-Emergent Adverse Events (TEAEs), and vital signs, will be summarized. No inferential analysis will be carried out for the safety data.

Shells for all tables and listing referred to in this section are displayed in separate document.

6.5.1 Adverse Events

Treatment-emergent AE (TEAE)s will be defined as AEs that occur on or after the date and time of study drug administration, or those that first occur pre-dose but worsen in frequency or severity after study drug administration. TEAEs will be captured through the end of the study. TEAEs and non-TEAEs (those occurring prior to administration of study medication or that first occurred prior to study drug administration and did not worsen in frequency or severity) will be listed.

The MedDRA[®] dictionary version 19.1 will be used to classify all AEs reported during the study by SOC and PT.

The relationship of TEAEs to study drug will be classified according to the study protocol as unrelated, unlikely, possible, or probable. The severity of AEs will be rated according to the study protocol as: mild, moderate, or severe.

An SAE is any untoward medical occurrence that:

- results in death,
- is life-threatening,
- requires inpatient hospitalization or prolongation of existing hospitalization,
- results in persistent or significant disability/incapacity,

- is a congenital anomaly/birth defect

A significant AE will be defined as any event (other than those reported as serious) that necessitated an intervention, including withdrawal of treatment, or significant additional concomitant therapy.

Serious and significant AEs will be listed separately.

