10. STUDY PROCEDURES

10.1. Schedule of Activities

The schedule of study activities is presented in [Table 3](#).

Table 3 Schedule of Activities

Evaluation	Screening	Visit 1
Written Informed Consent	X	
Inclusion/Exclusion Review	X	X ^a
Documentation of Disease	X	
Record/Review Concomitant Medications	X	X ^a
Medical History/ Demographics	X	
Height and Weight	X	
Vital Signs – HR, BP, RR		X ^b
Vital Signs – HR, BP, RR and temperature	X	X ^a
Comprehensive Physical Exam	X	
Brief Physical Exam		X ^b
Neurological Examination	X	
Brief Neurological Exam		X ^b
Eating Assessment Tool-10 (EAT-10)	X	X ^a
Functional Oral Intake Scale (FOIS)	X	X ^a
ALS Functional Rating Scale - Revised (ALSFRS-R)	X	X ^a
Oral Examination	X	X ^c
VFSS 1 - Penetration-Aspiration Scale (pre-dose)		X
VFSS 2 - Penetration-Aspiration Scale (post-dose)		X
Clinical laboratory evaluation(s)hematology, chemistry, urinalysis) ^d	X	X ^b
Urine Pregnancy Test (females of childbearing potential)	X	X ^a
Adverse Event	X	X ^c
Dispense Study Drug (one dose)		X

^aBefore VFSS 1 procedure

^bAfter VFSS 2 procedure

^cBoth – before VFSS 1 procedure and after VFSS 2 procedure

^dSee [Section 10.3.7 Laboratory Evaluations](#)

CONFIDENTIAL INFORMATION

The information in this study protocol is confidential. Any disclosure, copying or distribution of the information contained within is strictly prohibited without written consent from MonoSol Rx LLC.

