10.2.2. On-Study/On-Intervention Evaluations/Procedures

10.2.2.1. Baseline (Day 0, Visit 1):

The baseline visit (Day 0, Visit 1) will include a single dose of study drug. It will be scheduled within 28 days after the screening visit. At this visit, inclusion/exclusion criteria and concomitant medications will be reviewed. Vital signs, brief physical and neurologic examination, as well as study questionnaires and testing will be performed as noted in [Table-3; Schedule of Activities](#).

The following documentation and procedures will be performed at Day 0 (Visit 1):

- Adverse event review (before VFSS 1 procedure and after VFSS2 procedure)
- Inclusion/exclusion assessment (before VFSS 1 procedure)
- Concomitant medications (before VFSS 1 procedure)
- Urine pregnancy test for females of childbearing potential (before VFSS 1 procedure)
- Vital signs HR, BP, RR and temperature (before VFSS 1 procedure)
- Vital Signs HR, BP, RR (after VFSS 2 procedure)
- Oral Exam (before VFSS 1 procedure and after VFSS 2 procedure)
- Videofluoroscopy Swallow Study 1 (VFSS 1; pre dose procedure)
- Administer study drug (one dose)
- Videofluoroscopy Swallow Study 2 (VFSS 2; post dose procedure)

CONFIDENTIAL INFORMATION

The information in this study protocol is confidential. Any disclosure, copying or distribution of the information contained within is strictly prohibited without written consent from MonoSol Rx LLC.

- Brief physical exam (after VFSS 2 procedure)
- Brief neurologic exam (after VFSS 2 procedure)
- Clinical laboratory evaluation(s) see [Section 10.3.7 Laboratory Evaluations \(after VFSS 2 procedure\)](#)

Videofluoroscopy Swallow Study (VFSS 1-PAS)

Subjects will undergo a standardized videofluoroscopic swallowing study (VFSS) for direct visualization of the swallowing process and any episodes of penetration or aspiration. The VFSS represents the gold standard swallowing exam to directly visualize swallowing and specifically aspiration during swallowing. After consent has been verified and screens completed, the patient will be seated and will complete a standardized bolus protocol that includes 12 bolus trial presentations in the following order:

1. 5ml thin liquid barium
2. 5ml thin liquid barium
3. 5ml thin liquid barium
4. Regular sip of thin liquid taken from a cup containing 60cc of thin liquid.
5. Consecutive cup sips of remaining thin liquid barium
6. Tablespoon of thin honey consistency barium
7. Tablespoon of thin honey consistency barium

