10.2.5. Final On-Study Evaluations

The subject will be followed after Visit #1 for resolution of adverse events. If the subject decided to discontinue the study either after receiving the VFSS 1-PAS procedure but before receiving study medication or after receiving study drug and before VFSS 2- PAS procedure, the subject will be asked to comply with end of study clinical laboratory evaluation(s); see [Section 10.3.7 Laboratory Evaluations](#).

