10.2.7. Pregnancy

Women who are pregnant will not be enrolled in the study. Riluzole has not been studied in pregnancy and the Rilutek[®] US Package Insert notes that based on animal studies riluzole may cause fetal harm. Following administration of study drug, any known cases of pregnancy in female subjects or female partners of male subjects, will be reported until 30 days after the subject completes or withdraws from the study. The pregnancy will be reported immediately by phone and by faxing/emailing a completed Pregnancy Report to the

CONFIDENTIAL INFORMATION

The information in this study protocol is confidential. Any disclosure, copying or distribution of the information contained within is strictly prohibited without written consent from MonoSol Rx LLC.

Sponsor (or designee) within 24 hours of knowledge of the event. (Section 12.3; *Procedures for Reporting Adverse Events*)

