10.3.7. Laboratory Evaluations

Blood and urine specimens will be collected by qualified study center personnel at screening and visit 1 as described under *Section 10.0 Study Procedures* and sent to the lab for analysis. Clinical laboratory evaluation(s) are conducted at the screening visit and Visit 1 (after VFSS 2 procedure). A urine pregnancy test (females of child bearing potential only) will be conducted at the screening visit and at Visit 1 (before VFSS 1 procedure). The clinical laboratory evaluation(s) are presented in [Table 5](#).

If the subject decided to discontinue the study either after receiving the VFSS 1-PAS procedure but before receiving study medication or after receiving study drug and before the VFSS 2- PAS procedure, the subject will be asked to comply with end of study clinical laboratory evaluation(s) presented in [Table 5](#).

CONFIDENTIAL INFORMATION

The information in this study protocol is confidential. Any disclosure, copying or distribution of the information contained within is strictly prohibited without written consent from MonoSol Rx LLC.

Table 5 Clinical Laboratory Evaluation(s)

Hematology	Serum Chemistry	Urine
Complete Blood Count with Differential	Electrolytes	Urinalysis
	BUN	Pregnancy Test (females of childbearing potential)
	Creatinine	
	ALT	
	AST	
	Total Bilirubin	
	Albumin	

Abnormal laboratory test results or a positive urine pregnancy test will be flagged by the laboratory. All clinically important abnormal laboratory tests occurring during the study will be repeated if appropriate and followed until resolution (return to normal or baseline values) or stabilize, or until they are considered by the Investigator to be no longer clinically significant.

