11.1. Adverse Experience Reporting and Follow Up

Subjects will be instructed to inform clinic personnel of any untoward medical symptoms and/or events that may arise during the course of the study. If an adverse event is experienced by a subject, then the subject will be questioned concerning symptoms that may have occurred after the administration of the study drug. The incidence, severity and duration of all AEs will be recorded according to the following scale:

Mild	Adverse event resulting in discomfort, but not sufficient to cause interference in normal daily activities
Moderate	Adverse event resulting in discomfort that is sufficient to cause interference in daily activities.
Severe	Adverse event resulting in discomfort causing an inability to carry out normal daily activities

Subjects who withdraw due to an adverse event will be followed whenever possible until resolution of the adverse event. It may be appropriate for the subject to return to the site 2 weeks after the subject is off study to evaluate for resolution of any adverse events and to receive further information about options for future clinical care. The Investigator will decide the course of action.

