All serious adverse events (SAEs), whether or not the event is deemed drug-related, will be reported on the SAE Report Form by email or fax to the designated Clinical Research Organization, inVentiv Health within twenty-four hours of the Investigator being aware of SAE and inVentiv will report to the sponsor.

The safety address where SAE report forms and other SAE related documents should be sent is:

[contact]

Email: In case of emergency or fax failure the report can also be submitted by email to **[contact]**

If notification cannot be made via these means due to technical delivery problems, initial notification may be made by phone, using the inVentiv Health GSPV “SAE Hotline” number. A telephone call to the SAE hotline does not substitute for the site’s responsibility to submit a written SAE Report Form to inVentiv Health SAEs reported via the Hotline number must be followed with the SAE report the same day.

[contact]

In the event of any fatal or life-threatening SAE, the investigator must also inform a Medical Monitor at inVentiv Health by telephone or email:

[name] MPH Medical Director, Neuroscience Medical and Scientific Affairs [contact] Email: [contact]	[name] Medical Director [contact] Cellular: [contact] Email: [contact]
--	---

The Investigator will be responsible for notifying the IRB. The Sponsor will be responsible for notifying the regulatory agencies, as appropriate.

If a subject experiences a non-serious Adverse Event:

- All clinical adverse events are recorded in the CRFs designed specifically for this purpose. It is important to report all AEs, especially those that result in permanent discontinuation of the investigational product being studied, whether serious or non-serious.

CONFIDENTIAL INFORMATION

The information in this study protocol is confidential. Any disclosure, copying or distribution of the information contained within is strictly prohibited without written consent from MonoSol Rx LLC.

- The site should fill out the CRF and enter the non-serious AE information into the online Adverse Event Reporting System within 5 working days/7 calendar days of the site learning of a new AE or receiving an update on an existing AE.

Expected adverse events for riluzole are provided in Section 6.4; *Safety*.

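### Does it matter that SAP 6.5.1 does not date the end of treatment-emergent adverse event capture?

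*SAP*

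**What the plan says.** SAP 6.5.1 defines a treatment-emergent event by onset at or after the date and time of dosing, or by worsening after dosing. It then says that "TEAEs will be captured through the end of the study". It also promises listings of both treatment-emergent and other adverse events, with serious and significant events listed separately.

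The scheduled assessments stop at Visit 1. Footnote c of the Schedule of Activities (protocol 10.1, repeated in SAP 4) times the Visit 1 adverse event row "before VFSS 1 procedure and after VFSS 2 procedure". Protocol 10.3.7 gives the laboratory timing: "Clinical laboratory evaluation(s) are conducted at the screening visit and Visit 1 (after VFSS 2 procedure"). Neither schedule has a column after Visit 1.

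Three provisions reach past that visit. Protocol 10.2.5: "The subject will be followed after Visit #1 for resolution of adverse events". Protocol 11.1: "Subjects will be instructed to inform clinic personnel of any untoward medical symptoms and/or events that may arise during the course of the study". Protocol 11.3 has non-serious events entered "within 5 working days/7 calendar days of the site learning of a new AE" and serious events reported within 24 hours of awareness, with no closing date for either. Pregnancies, by contrast, "will be reported until 30 days after the subject completes or withdraws from the study" (protocol 10.2.7).

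**The concern.** The start of the treatment-emergent window is fixed to the time of dosing, but its end is a phrase with no date. A safety statement such as no events observed has meaning only over a stated period. Two readings seem possible: capture stops when the subject finishes Visit 1, or it runs on through the follow-up in protocol 10.2.5. The dated limit for pregnancy reports makes the silence on adverse events more noticeable. With so few subjects, one event more or less would show in a table. The worry is that the listings could depend on which reading the site or the analyst adopted, or that a reader could credit the study with a longer period of observation than it had.

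**Working it through.** No test, power or sample size figure bears on this point. The check sets the passages side by side and adds some day arithmetic.

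**1. Can the end of study be located from the documents?**
- SAP 6.5.4 times the final laboratory sample at early termination or end of study, and glosses the latter as after the second swallowing study. That is during Visit 1.
- SAP 3.1 expects about 30 days from screening to completion. Protocol 8.3 and 10.2 allow up to 28 days between screening and Visit 1. 30 − 28 = 2 days, so completion falls at or very near Visit 1.
- The last adverse event review in both schedules is at the same point.

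The three agree on a Visit 1 close. The gloss in 6.5.4 is written for laboratory timing and is not carried into 6.5.1, so this is an inference, but nothing in the documents contradicts it.

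**2. Do the follow-up provisions contradict that close?**
Protocol 10.2.5 and 11.2 concern following events to resolution, in 11.2 even when the subject is no longer participating. That is follow-up of known events. Neither section schedules an enquiry for new ones, so a Visit 1 close and later follow-up to resolution can both hold.

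**3. Does the pregnancy limit show a gap?**
Protocol 11.3 handles pregnancy as a separate process with its own report form, and says that a pregnancy is not processed as a serious adverse event. Its 30 days match the 30-day contraception commitment in the inclusion criteria. A dated limit for that process does not imply that adverse event capture should have the same one.

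**4. What happens to a late event?**
Suppose a non-serious event starts on Day 3 and the subject reports it.
- Classification: onset is after dosing, so it meets the 6.5.1 definition. The definition has no upper time limit.
- Display: once recorded, it is listed. Protocol 11.3 asks for onset time and duration, so a reader can see that it began after Visit 1.
- If serious, it is reported on awareness under protocol 11.3.

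The one open case is a late non-serious event that the site did not record because it took the study to have ended.

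**5. How large could the effect be?**
The SAP expects 7 + 2 = 9 completed subjects (SAP 1 and 6.2). One event in 9 is 1/9 = 11.1%. The proper denominator is the safety population of all dosed subjects (SAP 5.1), which the documents do not count and which could exceed 9 if someone was dosed and did not complete. SAP 6.5 and 6.5.8 rule out inferential analysis, so no test or error rate is touched. The swallowing scores come entirely from the two studies at Visit 1.

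**The case for a change.** The strongest case for a change is that the inference in step 1 borrows a laboratory gloss. Protocol 10.2.5 carries a heading about final on-study evaluations, which suggests that subjects remain on study after Visit 1. A Day 3 event could then be inside or outside capture, and one event is a visible share of a sample this small.

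The pharmacokinetics add to this. Protocol 6.3 puts peak concentration of the tablet at about 1.0 to 1.5 hours, with a mean half-life of 12 hours after repeated doses; five half-lives are 5 × 12 = 60 hours, or 2.5 days. The second swallowing study starts about three minutes after dosing. The documents do not give the length of Visit 1. If it ends within the first hour, scheduled enquiry stops before the peak.

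Part of this stands. Section 6.5.1 does not define its own closing point, and the scheduled adverse event and laboratory data describe tolerability soon after the dose. But the short observation comes from the visit schedule, not from the wording of 6.5.1, and both documents show it openly. A sentence in the SAP would not lengthen it. Borrowing the 30 days from pregnancy reporting would do harm: with no contact scheduled after Visit 1, a claim of no events through 30 days would imply surveillance that was never planned.

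**Conclusion.** This is a gap in wording that an analyst fills sensibly, and no change to the plan follows. The natural reading closes capture after the second swallowing study, or at early termination, for every dosed subject, with known events followed to resolution afterwards. Under either reading a recorded event is classified by the same onset rule and appears in the listings, with onset time reported. The primary swallowing comparison is unaffected, and no inference rests on the adverse event data.

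The residual effect is confined to a late, non-serious, spontaneously reported event that a site might not record. The documents give no figure for how often that would happen.

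The conclusion assumes that the gloss in SAP 6.5.4 reflects how the study team used the term, and that sites entered events they learned of, as protocol 11.3 requires.

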6.5.2 Physical and Neurological Examination

Subjects will undergo a comprehensive physical and neurological examination at screening, and a brief physical and neurological examination at Visit 1 following the second VFSS.

The comprehensive physical examination will include complete vital signs, weight, height, general appearance, and evaluation of systems: head, ears, eyes, nose, and throat; respiratory; abdomen; lymph nodes; spine; skin; cardiovascular; and extremities. The brief general physical examination will include abbreviated vital signs (blood pressure, heart rate, respiratory rate), and examination of the cardiovascular and respiratory systems and abdomen. Other elements may be included depending on symptoms or physical findings.

The comprehensive neurological examination will include (as permitted by the patient's capabilities) cranial nerves 2-12, muscle tone and strength, tendon reflexes and plantar response, sensory function (pain, light touch, position, vibration), coordination (finger-nose), and gait. The brief neurological examination will include cranial nerves 2-12, muscle strength, tendon reflexes, plantar response, and sensory function (pain, light touch, position, vibration). Other elements may be included depending on symptoms or physical findings.

Physical and neurological examination data will be listed separately by subject.

Any abnormal findings judged to be clinically significant will be documented as medical history or as an AE, depending upon whether noted at screening, prior to dosing or after dosing, as appropriate. Any physical examination or neurological examination findings documented as AEs will be included in the AE summaries.

6.5.3 Vital Signs

Complete vital sign measurements (blood pressure, heart rate, respiratory rate and temperature) will be performed at screening, and at Visit 1 pre-VFSS 1. The abbreviated vital sign measurements (blood pressure, heart rate, and respiratory rate) will be performed at Visit 1 post-VFSS 2.

Descriptive statistics (sample size, mean, median, SD, Min and Max,) for each vital sign parameter will be presented for screening, pre-VFSS 1, and post-VFSS 2. Unscheduled timepoints will be included in the listings but not in the summary tables except for baseline calculation if applicable. Descriptive statistics for change from baseline for post-VFSS 2 will also be presented. Baseline will be defined as the last non-missing result (scheduled or unscheduled) obtained prior to study drug administration. Results from post-dose repeat tests will not be included in the summary statistics unless the repeat was required (and documented as such) due to technical reasons or an invalid initial result.

A listing of all vital signs results will be provided.

